Lipid intake in the neonatal period is crucial for retinal and brain development along and an important source of calories for growth [16]. Due to this essential nature of lipid intake during the neonatal period, concern has been raised regarding lipid restriction and its effects on neonatal growth and neurodevelopmental outcomes. Studies investigating neurodevelopmental outcomes of infants treated with lipid restriction have shown development within normal ranges for the patient's age and similar to those of patients treated with standard soy-based lipid dosing [17, 18]. Studies have shown mixed results with regards to growth and neonates treated with lipid restriction. Rollins et al showed a greater increase in weight z-score for patients on standard soy-based dosing compared to reduced dosing, but found no difference in length or head circumference [13]. Other studies have found similar growth when comparing patients both in the neonatal period and into early childhood [18, 19]. The role of the various lipid strategies in the prevention of IFALD is still unclear at this time. Further studies are needed to better understand this disease, its prevention, and its outcomes. During this study we hope to compare two possible preventative strategies and determine a future direction for studying Smoflipid and soy-based lipid reduction.

Specific Aim

This study is designed to be a single center, pilot study to evaluate the prevention of cholestasis in neonates requiring abdominal surgery with intestinal failure, divided into two treatment groups, one receiving composite lipid emulsion (Smoflipid® 20%) at standard dosing and the other receiving soy-based lipid (Intralipid® 20%) at reduced dosing. The rate of cholestasis development in the two treatment groups will be compared to a historical control cohort which received soy-based lipid (Intralipid® 20%) at standard dosing of 2 to 3 g/kg/d .

Study Objectives

1. Primary: The primary objective of this study is to determine the number of infants receiving Smoflipid at typical dosing (2-3 g/kg/d) and the number of infants receiving Intralipid reduction (1 g/kg/day) that develop cholestasis compared to historical controls receiving Intralipid at standard dosing (2-3 g/kg/day). Cholestasis will be defined as direct bilirubin greater than 2 mg/dL for at least two measurements, 5-7 days apart.

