- AST or ALT greater than 5 times the upper limit of normal within 2 weeks of enrollment

- Direct bilirubin greater than 2 mg/dL on any consecutive measurement 5-7 days apart within 2 weeks of enrollment
- Severe coagulopathy with elevated INR greater than 2.0 or clinically significant bleeding as determined by the primary and research teams
- Culture confirmed sepsis with positive blood, urine, or CSF culture within 2 weeks (14 days) of enrollment
- Renal failure requiring dialysis
- Cyanotic heart disease requiring prostaglandin therapy
- Hypertriglyceridemia (greater than 250mg/dL) at time of enrollment

Enrollment/Randomization

A maximum total of 50 prospective patients, 25 per arm, will be enrolled in the study. Patients will be eligible for enrollment if they meet the above listed enrollment criteria. Once patients are determined to meet enrollment criteria, the parents of the patient will be approached and informed consent will be obtained. Please see separate informed consent document for full consent details.

Stratified randomization will be used to divide patients into each treatment group. Patients will be initially stratified based on the diagnosis of necrotizing enterocolitis or spontaneous intestinal perforation (ischemic/perforation group) or anatomic intestinal abnormality. Once stratified based on diagnosis, patients in each stratum will then be randomized to receive either Smoflipid or Intralipid reduction as described below. Group randomization will be based on premade concealed envelopes.

This study will not be blinded as the caloric dose of the lipid strategies will vary and potentially influence other TPN dosing. Both IV lipids will be given as a solution separate from the remaining TPN. This separate IV lipid will be given as two 12 hour infusions over a 24 hour period.

In the event of slower than anticipated patient enrollment, a minimum of 24 patients (12 per treatment group) will be enrolled in order to obtain needed feasibility data.

Historic Controls

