 - i. Each patient's chart will be reviewed for documentation of retinopathy of prematurity or bronchopulmonary dysplasia (chronic lung disease). The absence or presence of these diseases at the time of discharge will be noted for each study patient, particularly those patients born prematurely at less than 37 weeks gestation.
- d. Length of Stay:
 - i. An ICU length of stay will be calculated for each patient based on their admit date and discharge date from the Riley NICU.
 - ii. For patients transferred to another unit prior to discharge the transfer date will also be documented. For these patients a NICU length of stay and total hospital length of stay will be calculated.
- e. Laboratory monitoring (see Table 2 below for reference schedule):
 - i. Effort will be made to draw all study lab tests along with other standard of care, routinely scheduled labs.
 - ii. The schedule outlined here is a schedule of minimum laboratory work to be obtained. These studies may be obtained more often by the patient's primary clinical team. Any lab test obtained by the primary team within 3 days for weekly labs or within one week for less frequent labs will be used in place of the research lab test.
 - iii. Of note all lab tests listed could be considered standard of care, with the exception of INR.
 - iv. Essential fatty acid profiles will be obtained every 4 weeks (28 days) while receiving study lipid regimen.
 - 1. Blood volume needed 0.3-1mL
 - 2. Considered standard of care in any patient on alternative lipid dosing, such as patients enrolled in this study.
 - 3. If diagnosed with essential fatty acid disorder, defined as triene:tetraene ratio >0.05:
 - a. If Smoflipid dose is less than 3 g/kg/d, SMOF will be increased by 0.5 g/kg/d or to 3 g/kg/d maximum
 - b. Those receiving Smoflipid at 3 g/kg/d will be changed to Intralipid at current Smoflipid dose
 - c. Those receiving Intralipid will have their dose increased by 0.5 g/kg/d to maximum of 3 g/kg/d
 - v. Total and fractionated bilirubin levels will be monitored at least once weekly (7 days)
 - vi. Liver function panel and gamma-glutamyl transferase (GGT) will be monitored at least every 2 weeks (14 days).
 - vii. Triglyceride levels will be monitored within the first 48 hours of lipid initiation and then once weekly (7 days).

1. If triglyceride level >250 mg/dL will decrease dose of study lipid by 1g/kg/d to minimum of 2 g/kg/d of Smoflipid or 1 g/kg/d three days per week for Intralipid

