- ii) In adequate patient recruitment. We anticipate recruiting an average of 4 patients per study month. If there is a significant lag and will be unable to obtain our full number of patients within a reasonable time, this will be reason to terminate the study early.
- b) Principle investigators will consider study cessation if SAEs occur within a specific treatment arm out of proportion to what would be expected from typical disease course.

Statistical Considerations

Our goal is to recruit 25 patients into each group. Given this is a pilot study, the minimum number needed per arm would be 12 patients as per published statistician recommendations [21]. The reasoning for using a pilot study include determining the feasibility of performing a larger scale study. Performing a pilot study prior to the large-scale study will give us information on patient recruitment and retention, along with design flaws that may be remedied prior to future studies.

All data will be summarized by group at each time point; summaries will include frequencies and proportions for categorical variables and mean, standard deviation, and range for continuous variables. Distributions of continuous variables will be examined. Parenteral nutrition characteristics will be recorded and tabulated. Tabulated categorical outcomes will include: proportions of subjects with cholestasis or IFALD, essential fatty acid deficiency, enteral autonomy at end of study, retinopathy of prematurity, chronic lung disease, and adverse events. Tabulated continuous measurements will include: growth rates, essential fatty acid profile, total caloric intake, percentage of calories from enteral intake, time to enteral autonomy, lipid dose delivered, bilirubin level, liver enzymes, gamma-glutamyl transferase (GGT), triglycerides, and length of stay. Fisher's Exact Tests will be used to compare between groups for categorical variables. Time to enteral autonomy will be evaluated using Kaplan-Meier survival curves and a log-rank test. Mixed models will be used to compare between groups and compare within groups over time for continuous variables measured throughout the study. Length of stay will be compared using a Wilcoxon Rank Sum test. A 5% significance level will be used for all tests mentioned.

Privacy/Confidentiality Issues

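### The cholestasis comparison takes no account of direct bilirubin at entry, so an entry difference from the historic controls passes into the result and some precision may be lost

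*Combined protocol and SAP*

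**What the plan says.** Study Objectives, item 1, defines the outcome: "Cholestasis will be defined as direct bilirubin greater than 2 mg/dL for at least two measurements, 5-7 days apart". The Specific Aim names the main contrasts: "The rate of cholestasis development in the two treatment groups will be compared to a historical control cohort".

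Statistical Considerations lists the outcome among the categorical ones ("Tabulated categorical outcomes will include: proportions of subjects with cholestasis or IFALD") and gives one method for these: "Fisher's Exact Tests will be used to compare between groups for categorical variables". It adds: "A 5% significance level will be used for all tests mentioned". No covariate, stratum or adjusted sensitivity analysis is named. The mixed models are for continuous repeated measures.

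Entry bilirubin appears in four places:
- **Exclusion criteria.** Infants are excluded for "Direct bilirubin greater than 2 mg/dL on any consecutive measurement 5-7 days apart within 2 weeks of enrollment". Lower values, or a single higher one, do not exclude.
- **Laboratory monitoring and Table 2.** Bilirubin is due at least weekly. Table 2 shows a hepatic panel at week 0, and fractionated bilirubin by name only in alternate weeks. The panel must therefore carry direct bilirubin in the other weeks, which is an inference.
- **Historic Controls (selection).** The same exclusions are applied at abdominal surgery. Matching, where possible, is on lipid days, diagnosis, gestation at birth and birth weight.
- **Historic Controls (data collection).** Laboratory values are recorded only where the electronic record has them.

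Randomisation is stratified by diagnosis group only.

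**The concern.** The outcome is a threshold on a variable that already has a value at entry. Fisher's test treats an infant entering at 1.9 mg/dL and one entering at 0.2 mg/dL as equally likely to cross 2 mg/dL. This has two consequences.

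The first is confounding. Each prospective arm is compared with controls who were not randomised against it and were not matched on bilirubin. If the groups start at different levels, the crude difference in cholestasis contains that starting difference. It could create an apparent benefit or hide a real one. Between the two randomised arms the same mechanism is only chance imbalance.

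The second is precision. If entry bilirubin predicts cholestasis, leaving it out wastes information in a study with at most 25 infants per arm.

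The study is meant to guide the choice of strategy for later work, so a distorted contrast could misdirect the next trial.

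**Working it through.** **Inputs from the documents.** There are 25 infants per prospective arm ("A maximum total of 50 prospective patients, 25 per arm, will be enrolled in the study"), a minimum of 12 per arm, and 24 historic controls. The significance level is 5%; sidedness is not stated and two-sided is assumed. The totals agree: 2 × 25 = 50 and 2 × 12 = 24. The documents give no cholestasis rate, effect size or power, so there is no power figure to reproduce.

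**Assumptions.** All rates, correlations and shifts below are assumed. Entry bilirubin X is standard normal. Cholestasis occurs when Z = ρX + √(1 − ρ²)·e exceeds a threshold that gives the group its assumed rate. Firth models are tested by penalised likelihood ratio at 5%.

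**Step 1: precision.** Cholestasis is assumed in 50% of controls and 20% of treated infants. Unadjusted Firth is shown so that the change of test is not credited to the covariate.

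| Controls v treated | ρ | Fisher | Firth, unadjusted | Firth, adjusted | Due to covariate |
|---|---|---|---|---|---|
| 24 v 25 | 0.3 | 0.57 | 0.58 | 0.61 | 0.61 − 0.58 = 3 points |
| 24 v 25 | 0.5 | 0.57 | 0.58 | 0.66 | 0.66 − 0.58 = 8 points |
| 24 v 25 | 0.7 | 0.59 | 0.60 | 0.75 | 0.75 − 0.60 = 15 points |
| 24 v 12 | 0.3 | 0.36 | 0.41 | 0.42 | 0.42 − 0.41 = 1 point |
| 24 v 12 | 0.5 | 0.36 | 0.42 | 0.48 | 0.48 − 0.42 = 6 points |

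Repeat runs at 24 v 25 and ρ = 0.5 gave adjusted power from 0.66 to 0.69. The simulation standard error with 1,500 trials is √(0.66 × 0.34 / 1500) = 0.012, so about 8 to 10 points is a fair summary. At 24 v 12 and ρ = 0.5, repeat runs put the covariate's share at about 4 to 6 points. With no true effect (40% in both groups), the adjusted test rejected in 4.1% to 6.5% of trials.

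A second set-up used a logistic outcome model at 24 v 25. The variance of the risk difference fell by about 2–5%, 13–14% and 25% when entry bilirubin discriminated with an AUC of 0.64, 0.74 and 0.82. With no prognostic value (AUC 0.50) it rose by 1–3%.

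**Step 2: entry difference.** Suppose there is no true effect, the base rate is 40%, and controls enter δ = 0.5 SD higher. The control rate becomes Φ(Φ⁻¹(0.40) + ρδ), with Φ⁻¹(0.40) = −0.253:
- ρ = 0.3: Φ(−0.253 + 0.15) = Φ(−0.103) = 0.459, a spurious difference of 0.40 − 0.459 = −6 points.
- ρ = 0.5: Φ(−0.253 + 0.25) = Φ(−0.003) = 0.499, a spurious difference of −10 points.

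At ρ = 0.5, simulation put Fisher's false-positive rate at 0.11, against 0.045 after adjustment. The logistic set-up agrees: spurious differences of −6, −10 and −13 points and Fisher false-positive rates of 0.06, 0.10 and 0.14 at AUC 0.64, 0.74 and 0.82. After adjustment the mean difference was about 0 and rejection was 0.05–0.06. A shift of 0.3 SD gave −3, −6 and −8 points.

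**Step 3: room for a covariate.** Expected events at 50% v 20% are 24 × 0.5 + 25 × 0.2 = 17, or 24 × 0.5 + 12 × 0.2 = 14.4 at the minimum size. That supports one extra term with penalisation, not several.

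**The case against.** **This is a pilot.** Its stated purpose is feasibility, its minimum size comes from a rule of thumb, and it claims no power. That stands: no figure in the plan becomes wrong. But the plan does test cholestasis against controls at 5%, and the contrast can mislead whatever the power.

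**Entry bilirubin is partly handled already.** Data are summarised by group at each time point, bilirubin level is a listed continuous measure, controls are matched and randomisation is stratified. These would show an imbalance, or balance other factors. None brings entry bilirubin into the cholestasis comparison.

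**The gain rests on an unstated correlation.** That stands. The simulations also use an unbounded covariate, whereas the exclusion largely limits entry values to about 2 mg/dL, which may weaken its prognostic value. At 12 per arm and correlation 0.3, the covariate adds about 1 point.

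**The proposed model leaves out diagnosis and the matching factors.** True, but with about 14 to 17 expected events one covariate is a defensible limit, and bilirubin is the variable from which the outcome is built.

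**An adjusted odds ratio answers a different question from the crude proportions.** Fair. That is why Fisher's test should stay and a standardised risk difference should accompany the model.

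A reader might infer that direct bilirubin is measured at entry in every infant. The documents do not support this. Control values depend on the record, and the exclusion does not itself require a measurement: an infant with one value or none is not excluded by it.

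**Conclusion.** The point holds in a limited form. The planned cholestasis comparison ignores entry direct bilirubin, and nothing else in the plan brings it in. In the contrasts with historic controls an entry difference is confounding; between the randomised arms it is chance imbalance. The precision at stake runs from about nil to about 8 to 10 points of power at correlation 0.5 with 24 v 25, and about 4 to 6 points at 24 v 12. The possible distortion is about 6 to 10 percentage points for a 0.5 SD entry difference at correlations of 0.3 to 0.5. All of this rests on assumed rates, correlations and shifts.

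Two stronger readings go too far. One is that adjustment would remove the confounding. Controls are assessed at surgery and prospective infants at enrolment, so the covariate may be taken at different points in the illness, and other differences between the periods remain. The other is that the groups do differ at entry: the documents leave room for a difference but do not show one.

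**What to change.** In Statistical Considerations, keep Fisher's exact test as the unadjusted comparison and add the following for each contrast (Smoflipid v controls, reduced Intralipid v controls, arm v arm):

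- **Model.** Firth-penalised logistic regression for cholestasis with group and entry direct bilirubin. Entry is the last value before study lipid for prospective infants, and the last value at or before surgery for controls.
- **Reporting.** The adjusted odds ratio with a profile-penalised-likelihood 95% interval, and a standardised risk difference with a bootstrap 95% interval.
- **Missing values.** Report the number missing by group, use the available values, and run a multiple-imputation sensitivity analysis.
- **Interpretation.** State that adjustment reduces but does not remove confounding with historic controls, because their entry point is surgery rather than enrolment.
- **Table 2.** Confirm that the week 0 hepatic panel includes direct bilirubin.

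The cost is wording and programming, with no extra infants and no change to care. The downsides are one more model term with few events, control records that may lack the value, and a variance increase of about 1–3% if entry bilirubin proves uninformative.

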2. Secondary (comparison of each listed parameter between the prospective treatment groups in addition to comparison of each treatment group with historic controls):
 - a. Growth (rate of change)

- i. Weight, length, and head circumference at enrollment, on a weekly basis while receiving study lipid, and 2-3 weeks post-study lipid completion.
- ii. Weight, length, and head circumference at 36 weeks corrected gestational age and time of discharge.
- b. Essential fatty acid profile differences and development of deficiency
- c. Average total caloric intake for all patients on weekly basis
 - i. Average lipid dose delivered on weekly basis
- d. Feeding tolerance/ percentage of total calories from enteral feeds
 - i. Time to achievement of enteral autonomy (full enteral feedings)
 - ii. Percentage of enteral calories at end of study
 - iii. Percentage of patients in each group with enteral autonomy
- e. Transaminase, alkaline phosphatase, GGT levels at enrollment, every 4 week time point, and end of study
- f. Triglyceride concentration at baseline, weekly, and end of study
- g. Rates of other diagnoses in each study group
 - i. Retinopathy of prematurity as diagnosed by Ophthalmologic examination
 - ii. Chronic lung disease as defined by need for oxygen at time of discharge or 36 weeks corrected gestational age (if at least 28 days of age), whichever comes first.
- h. Rates of adverse and serious adverse events in each group
- i. Length of stay
- j. Two year neurodevelopmental differences using ASQ-3 screening

Study Population

Inclusion criteria

Infants admitted to the Riley Hospital Neonatal Intensive Care Unit (NICU), regardless of postmenstrual or corrected gestational age, with anticipated need for parenteral nutrition for four or more weeks PLUS one or more of the additional inclusion criteria listed below will be eligible for inclusion within the study and for randomization. Inclusion criteria include:

- Anatomic intestinal defect: Neonate with intestinal atresia, omphalocele, gastroschisis or volvulus with or without intestinal resection and need for parenteral nutrition pre or post-operatively.
- Ischemic/perforation intestinal injury: Neonates with spontaneous intestinal perforation or necrotizing enterocolitis requiring surgical intervention with need for parenteral nutrition post-operatively.

Exclusion criteria at time of study enrollment

- Infant with current weight less than 750 grams

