A group of 24 patients previously treated in the Riley NICU from the years 2016 – 2017 will be used as a historic control cohort. Historic patients will be eligible for enrollment in the study if they have one of the above listed diagnoses, received post-operative parenteral nutrition, and were treated with soy-based lipid at standard dosing (2-3 g/kg/day). Historic patients will be ineligible to participate if any of the above listed exclusion criteria are true at the time of their abdominal surgery. Historic patients will be matched to prospective patients when able. This matching will first utilize in order: 1. days of parenteral lipid therapy, 2. diagnosis, 3. birth gestational age, and 4. birth weight when selecting for inclusion.

Study Procedures

1. Smoflipid® (20% lipid emulsion) treatment group
 - a. Advancement:
 - i. Smoflipid will be started at 1 g/kg/d on day 1 of parenteral nutrition after enrollment and advanced by 1 g/kg/d each subsequent day to a goal maximum of 3 g/kg/d
 - b. Maintenance and weaning [8]:
 - i. The Table below will be used as a guide for weaning Smoflipid as enteral nutrition is initiated and advanced.
 - ii. Patients will continue to be monitored by a clinical dietitian and pharmacist as per standard of care. Pending their recommendations, along with the clinical state of the child, the actual dose of Smoflipid needed may vary by individual patient.
 - c. Other parenteral nutrition components
 - i. Amino acid will be provided to meet estimated protein requirements only and will not be increased as a form of caloric intake.
 1. Term infant approximate goal of 3 g/kg/day and preterm infant approximate goal of 3.5 – 4 g/kg/day.
 - ii. Glucose infusion will be utilized and advanced per standard protocol to provide remainder of estimated non-protein caloric need of each individual patient.
 1. Maximum glucose infusion rate (GIR) while enrolled in study of 16 mg/kg/min. If further caloric intake is required, Smoflipid will be increased to a maximum of 3 g/kg/d.

Table 1: Smoflipid dosage recommendations for weaning as enteral feeds advanced

% calories from PN	Volume enteral feeds (ml/kg/d)	Enteral calories (kcal/kg/d)	Lipid (g/kg/d)
80-100%	\leq 20-40	\leq 30	3
60-80%	40-60	30-40	3
50-60%	60-80	40-50	2.5
40-50%	80-100	50-60	2
30-40%	100-110	60-70	1.5
20-30%	120	70-90	1
<20%	>120	>90	0

2. Intralipid® (20% lipid emulsion) reduction treatment group
 - a. Advancement:
 - i. Intralipid:

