	Blood Volume (mL)	3.1	2.8	0.8	2.2	1.7	0.5	0.8	2.2	1.7	0.5	0.8	2.2	1.7

f. Neurologic Follow-up:

i. ASQ-3 at 2 years of age:

1. All prospective patients will have an ASQ-3 obtained during the 2nd year of life (age 2 year 0 day to 2 year 364 days).
2. ASQ-3 will be obtained in one of three manners:
 - a. In person: if patient has previously scheduled appointment at Riley
 - b. Via phone: if able to confirm identity of parent or guardian
 - c. Via mail (electronic or standard): if able to confirm proper mailing address of patient and parent/guardian
3. ASQ-3 will be completed by the subject's parent or guardian with the aid of one of the primary investigators.
4. If the subject receives a score within the "monitoring zone" or below threshold of "normal" in any developmental area:
 - a. Parent/guardian will be notified of this score
 - b. If known developmental delays exist will document if patient is receiving services for delay.
 - c. If no previously known developmental delay will refer patient to their primary care physician for further developmental screening and referral for proper services and follow-up.

g. Stopping study Lipid:

- i. Once a study subject reaches one of the following parameters they will stop receiving study lipid, whichever parameter occurs first:
 1. Maximum time of 12 weeks (84 days).
 2. Cholestasis with direct bilirubin of ≥ 3 mg/dL on two consecutive lab draws at least 5-7 days apart.
 3. Lipid or parenteral nutrition discontinuation for more than one week (7 days).
 4. Subject is discharged home or transferred from Riley Hospital for Children.

- ii. Once a subject reaches one of these time points, their lipid treatment, including lipid choice and dose, will be at the discretion of their primary treating physician.
- iii. Subjects will continue to be followed by the research team in order to have the following information documented:
 - 1. Anthropometric measurements at 36 weeks corrected gestational age.
 - 2. Follow-up anthropometric measurements at 2 – 3 weeks after stopping study lipid or at the time of discharge.
 - 3. Follow-up laboratory testing at 2 – 3 weeks after stopping study lipid if still admitted to Riley Hospital for Children.
 - 4. Documentation of prematurity complications.
 - 5. Discharge and/or transfer date to determine length of stay.
 - 6. ASQ-3 screen during the second year of life.

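### Diagnosis group defines the randomization strata but appears in none of the analyses, which leaves the non-randomized primary comparison open to bias from diagnosis mix

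*Combined protocol and SAP*

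**What the plan says.** - **Enrollment/Randomization:** "Stratified randomization will be used to divide patients into each treatment group". The strata are ischemic/perforation (necrotizing enterocolitis or spontaneous perforation) and anatomic abnormality.
- **Specific Aim:** "The rate of cholestasis development in the two treatment groups will be compared to a historical control cohort". The primary objective makes the same comparison.
- **Study Objectives, secondary:** "comparison of each listed parameter between the prospective treatment groups in addition to comparison of each treatment group with historic controls".
- **Historic Controls:** "Historic patients will be matched to prospective patients when able", and "This matching will first utilize in order: 1. days of parenteral lipid therapy, 2. diagnosis", followed by birth gestational age and birth weight. There are 24 controls, from 2016–2017.
- **Statistical Considerations:** Fisher's "Exact Tests will be used to compare between groups for categorical variables"; Wilcoxon rank sum for length of stay; mixed models for repeated continuous measures; and, for the one time-to-event outcome, "Time to enteral autonomy will be evaluated using Kaplan-Meier survival curves and a log-rank test"; 5% significance throughout. No stratum, diagnosis covariate or matched-set analysis is named here or elsewhere.

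**The concern.** By stratifying on diagnosis group, the protocol treats it as worth balancing. Stratification secures that balance between the two randomized arms, but the primary comparison is not between those arms. It sets each arm against historic controls, where only matching protects the diagnosis mix. That matching is conditional, ranks diagnosis second, and draws on one set of 24 controls for up to 50 prospective infants, so one-to-one matching is impossible at full enrollment. A pooled Fisher test and a pooled risk difference absorb whatever imbalance remains. If controls contain more of the higher-risk diagnosis, a lipid strategy looks better than it is; if fewer, a real benefit is hidden.

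For the randomized comparisons the issue is smaller. Ignoring the strata does not bias them, but it makes the tests conservative and costs power when diagnosis is prognostic.

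**Working it through.** **The plan's own figures.** 2 × 25 = 50 and 2 × 12 = 24 agree with the stated totals. The sample size rests on a pilot rule of thumb, so there is no power calculation to reproduce.

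**Inputs from the documents.** 25 per arm (minimum 12), 24 controls, 5% level (two-sided assumed), two diagnosis groups.

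**Assumed inputs.** Arm split 13 anatomic + 12 ischemic (6 + 6 at the minimum). Anatomic/ischemic cholestasis risks 30/50, 20/60 or 10/70%. Anatomic controls 12, 9, 5 or 15 of 24.

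**Bias with no true effect.** Bias = expected pooled control risk − expected pooled arm risk = (ischemic share of controls − ischemic share of arm) × (risk gap). With 9 of 24 anatomic controls and 10/70% risks:

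(9 × 0.10 + 15 × 0.70)/24 − (13 × 0.10 + 12 × 0.70)/25 = 47.5% − 38.8% = 8.7 points.

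**Type I error.** Exact enumeration of all outcomes compared pooled Fisher with an exact conditional test stratified by diagnosis (convolution of the two stratum hypergeometric distributions). The three values in each cell are for 30/50, 20/60 and 10/70%.

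| Anatomic controls | Bias (points) | Fisher error (%) | Stratified exact error (%) |
|---|---|---|---|
| 12/24 | 0.4, 0.8, 1.2 | 3.6, 2.5, 1.0 | 3.8, 3.3, 3.1 |
| 9/24 | 2.9, 5.8, 8.7 | 4.2, 4.3, 4.0 | 3.7, 3.4, 3.1 |
| 5/24 | 6.2, 12.5, 18.7 | 6.0, 11.2, 20.0 | 3.2, 3.2, 3.0 |

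At 9/24 the errors fall mostly on the false-benefit side: 3.2, 4.0 and 4.0% against a nominal 2.5%. In simulation the Mantel-Haenszel risk difference is unbiased in all nine cases.

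**Power with a true within-stratum odds ratio of 0.25.**

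| Anatomic controls | Fisher (%) | Stratified exact (%) |
|---|---|---|
| 12/24 (mix held) | 46, 40, 27 | 48, 46, 40 |
| 15/24 (opposite mismatch) | 39, 26, 10 | 44, 40, 33 |

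**Minimum arm of 12, no effect.** Bias is 2.5–7.5 points at 9/24 and 5.8–17.5 at 5/24. Fisher error is 1.7–2.8% and 3.7–6.6%; the stratified exact test gives 2.3–3.0%.

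**Randomized arms (13 + 12 each), between-arm endpoints the plan lists, by simulation.**

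- Length of stay (0.8 SD effect on the log scale; stratum shift 0, 0.5, 1 SD): Wilcoxon 77, 75, 68%; van Elteren 76, 76, 76%.
- Enteral autonomy (hazard ratio 2; stratum hazard ratio 1, 0.5, 0.33; assumed 8-week median in the faster stratum of the reference arm; censored at 12 weeks): log-rank 57, 45, 37%; stratified log-rank 56, 48, 45%.

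**The case against.** **Matching may be enough.** Controls must have the same eligible diagnoses, and a two-level factor is among the easier ones to match. If the mix holds, bias is at most 1.2 points and Fisher error is not inflated. This stands, but the plan neither guarantees nor reports that balance, and stratifying still gains 2 to 12 points of power in that case (rounded figures).

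**The chance of a mismatch is unknown.** This stands. If controls were drawn without regard to diagnosis, 9 or fewer anatomic of 24 would occur with probability 15% from a pool that is 50% anatomic and 69% from a 35% pool; for 5 or fewer the figures are 0.3% and 10%. The plan does consider diagnosis, so these figures do not show how likely a mismatch is under its matching rule.

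**The bias is small beside a pilot's imprecision.** At about 39% risk the standard error of the difference is √(0.39 × 0.61 × (1/25 + 1/24)) ≈ 14 points, so 3 to 9 points is roughly 0.2 to 0.6 standard errors. This is fair, and it limits the severity. But the study is meant to guide later work, and the bias has a direction that more patients would not remove.

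**The mixed models could include diagnosis.** They could; the plan simply names no such term.

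**The randomized part is only about efficiency.** Agreed. The gain vanishes when diagnosis is not prognostic.

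**Conclusion.** The concern holds, as an improvement to consider rather than a fatal flaw. As written, the primary comparison has no protection against diagnosis mix except matching that may not be achieved. Under the assumed risks, the bias is negligible if the mix holds and 3 to 9 points under a moderate mismatch, without inflating two-sided Fisher error. Error rises clearly above 5% only when a severe mismatch coincides with a strongly prognostic diagnosis. A mismatch in the opposite direction costs substantial power. The between-arm comparisons remain valid. All magnitudes depend on stratum risks, an arm split and a control mix that the documents do not give. Stratifying removes bias from diagnosis mix only, not other differences between historic and current patients.

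**What to change.** State in Statistical Considerations that analyses use the diagnosis groups that defined randomization:

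- **Cholestasis and other categorical outcomes,** historic and between-arm: exact conditional test stratified by diagnosis group, with a Mantel-Haenszel risk difference and 95% CI.
- **Enteral autonomy:** stratified log-rank test.
- **Length of stay:** van Elteren test.
- **Mixed models:** diagnosis group as a fixed effect.
- **Historic comparison:** report the balance achieved on all four matching factors. Adjust for birth gestational age and birth weight in a sensitivity analysis only, since events will be few.

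Do not adjust for days of lipid therapy. The stopping rule ends study lipid for "Cholestasis with direct bilirubin of ≥ 3 mg/dL on two consecutive lab draws at least 5-7 days apart", so in the prospective arms this variable can partly reflect the outcome. The link is incomplete: the endpoint threshold is lower (above 2 mg/dL), non-study lipid may continue afterwards, and the rule is not stated for controls. Stratifying by diagnosis does not resolve any problem from matching on it.

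**Cost.** SAP wording and slightly more analysis; diagnosis is already recorded for randomization and for control eligibility. If diagnosis is not prognostic (40/40%, odds ratio 0.25, 25 versus 24), Fisher has 48% power and the stratified exact test 48, 47 and 42% at 12, 9 and 5 of 24 anatomic controls, a loss of 0, 1 and 6 points. The Mantel-Haenszel interval (Sato variance) covers 93–95% at 25 per arm and 91–93% at 12 per arm, so it is slightly short at the minimum size.
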